7.5.3 Dose Modifications or Escalations

If cisplatin dose is held due to toxicity, CBC should be repeated weekly until counts recover to minimum levels required to resume treatment. If the dose of cisplatin is delayed more than 21 days because of hematologic or renal adverse events, that dose will be omitted.

7.5.3.1 Hematologic Toxicity

If on the day of scheduled treatment with cisplatin the absolute neutrophil count (ANC) is < 1200, hold treatment until ANC \geq 1200, then treat at 100% dose. Neutropenic fever will require permanent 25% dose reduction. Per CTCAE, v. 4.0, febrile neutropenia is fever of unknown origin without clinically or microbiologically documented infection; ANC < 1.0 x 10e9L, fever > 38.5°C.

Thrombocytopenia: If on the day of scheduled treatment with cisplatin the platelet count is <75,000, hold treatment until platelets are > 75,000, then treat at 100% dose. Thrombocytopenia that results in bleeding will require a 25% dose reduction.

7.5.3.2 Non-Hematologic Toxicity

Renal Adverse Events: Cisplatin should be administered on the scheduled day of treatment using the following guidelines: If creatinine is > 1.2 mg/dl, clearance must be done in order to make dose adjustment. If the calculated nomogram is 50 mL/min or above, a 24-hour urine collection is not needed, but if the nomogram calculation is less than 50 mL/min, a 24-hour urine collection is mandated.

| Creatinine clearance | Cisplatin dose |
|----------------------|---------------------------|
| > 60 mL/min | 100 mg/m ² |
| 40-50 mL/min | 50 mg/m ² |
| < 40 mL/min | Discontinue and notify PI |

Neurotoxicity: If any signs of grade 3 or greater neurotoxicity occur, discontinue cisplatin. The radiation therapy will continue.

Mucositis: Grade 4 will require a 25% dose reduction

Ototoxicity: For new clinical hearing loss not requiring a hearing aid or for tinnitus that interferes with activities of daily living, treat at 50% dose reduction. For hearing loss requiring a hearing aid, discontinue cisplatin. If the physician is unsure about the severity of the hearing loss, an audiogram is encouraged.

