7.5.2 Treatment Administration

Patients who do not respond to or progress through neoadjuvant cetuximab will receive cisplatin, 100 mg/m², administered intravenously on approximately Days 1, 22 and 43 of radiation therapy. Days of administration may vary up to two days, and may vary longer if necessary due to toxicity. Alternatively, at the treating medical oncologist's discretion, the patient may instead receive weekly cisplatin 40 mg/m². Note that in order to receive the full dose cisplatin 100 mg/m², the original GFR must be > 60 ml/min. To receive the cisplatin 40 mg/m², the original GFR must be > 50 ml/min.

High dose cisplatin is a highly emetogenic regimen with significant incidence of delayed nausea and vomiting. Institutional guidelines for highly emetogenic regimens

should be followed. In the absence of such guidelines:

For acute nausea and vomiting, premedication should include a 5-HT3 antagonist, such as granisetron, ondansetron, or palonosetron, plus a corticosteroid, such as dexamethasone, up to 20 mg *i.v.*. Breakthrough nausea and vomiting should be managed at the discretion of the medical oncologist or radiation oncologist. Delayed nausea and vomiting (greater than 24 hours after chemotherapy administration) may be managed by the addition of aprepitant concurrently or with metoclopramide and dexamethasone.

Patients must receive vigorous hydration and diuresis. A suggested regimen is prehydration with a 1 liter of D5N S over 2-4 hours and mannitol, 12.5 g *i.v.* bolus immediately prior to cisplatin. Then cisplatin, 100 mg/m², in 500 ml NS is administered over 1-2 hours with an additional 1 to 1.5 liters of fluid given post-hydration. Any pre-existing dehydration must be corrected prior to cisplatin administration. Should extravasation occur, the treating physician should follow institutional guidelines for management. Overnight hospitalization for hydration after cisplatin is strongly encouraged if it is allowed by the patient's insurance company. Additional *i.v.* hydration and BUN/creatinine check should be strongly considered later in the week after cisplatin administration, in order to prevent dehydration and severe fluid/electrolyte imbalance.

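### The renal dose table for cisplatin (7.5.3.2) names no regimen and fits only the three-weekly schedule, so weekly patients at 40–50 mL/min have no usable reduced dose

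*Combined protocol and SAP*

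**What the plan says.** Two cisplatin regimens are permitted with radiation. Section 7.2.7 prefers 100 mg/m² every three weeks and lets the treating medical oncologist choose 40 mg/m² weekly instead; 7.5.2 and 7.5.6 repeat this. The three-weekly doses are "administered intravenously on approximately Days 1, 22 and 43 of radiation therapy". Section 7.5.2 also sets starting thresholds on the original GFR: above 60 mL/min for 100 mg/m², above 50 mL/min for 40 mg/m².

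On-treatment renal adjustment is in 7.5.3.2, under Renal Adverse Events. It opens with "Cisplatin should be administered on the scheduled day of treatment using the following guidelines" and names no regimen. Its parts are:

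- A trigger: "If creatinine is > 1.2 mg/dl, clearance must be done in order to make dose adjustment".
- A measurement rule: "if the nomogram calculation is less than 50 mL/min, a 24-hour urine collection is mandated".
- A table giving 100 mg/m² above 60 mL/min, then "40-50 mL/min | 50 mg/m"² for the reduced-dose band, and below 40 mL/min "Discontinue and notify PI".

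The neighbouring cisplatin reductions are written as percentages. For ototoxicity short of a hearing aid the instruction is to "treat at 50% dose reduction". In 7.5.3.1, "Neutropenic fever will require permanent 25% dose reduction". Bleeding with thrombocytopenia and grade 4 mucositis are handled the same way.

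**The concern.** A dose-reduction table for a nephrotoxic drug should give a lower dose as clearance falls, under every regimen the protocol allows. This one is in absolute mg/m² and carries no regimen label. Its reduced dose is higher than the scheduled weekly dose, so it cannot serve weekly patients as printed, and no other section supplies a weekly figure.

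The gap sits where it is likely to be needed. A patient whose original GFR is above 50 and up to 60 mL/min may start cisplatin only on the weekly regimen, and 40–50 mL/min is the band directly below that entry threshold. Section 17.2 lists renal damage among the cisplatin risks. Section 6 schedules serum chemistries, including creatinine, weekly during radiation, so the rule can come into play on any weekly dosing day.

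What is at stake is patient safety and consistent dosing in the non-responder cohort.

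**Working it through.** **Inputs**

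- Scheduled doses: 100 mg/m² every three weeks, or 40 mg/m² weekly (7.2.7, 7.5.2).
- Table dose at 40–50 mL/min: 50 mg/m²; above 60 mL/min: 100 mg/m² (7.5.3.2).
- Allowed variance: 10% of the calculated dose (7.5.1).
- Length of radiation: 6–7 weeks (7.4.2).
- Planned total 27, of whom 16 are cetuximab responders, from an assumed 60% response (16.2).

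**Table dose against scheduled dose**

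Ratio = table dose / scheduled dose.

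| Clearance row | Three-weekly (100 mg/m²) | Weekly (40 mg/m²) |
|---|---|---|
| > 60 mL/min, 100 mg/m² | 100/100 = 1.00 | 100/40 = 2.50 |
| 40–50 mL/min, 50 mg/m² | 50/100 = 0.50 (−50%) | 50/40 = 1.25 (+25%) |

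Both dose rows make sense for the three-weekly regimen and neither does for the weekly one. The 25% excess is not covered by the variance allowance, whose ceiling for a weekly dose is 40 × 1.10 = 44 mg/m².

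**Dose per three weeks at 40–50 mL/min**

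- Three-weekly patient following the table: 50 mg/m².
- Weekly patient on the unreduced schedule: 3 × 40 = 120 mg/m².
- Weekly patient following the table literally: 3 × 50 = 150 mg/m².

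**If the table is read as three-weekly only**

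The text then sets no weekly dose at 40–50 mL/min, and the compatible range is 0 (hold) to 40 mg/m² (no change). Three other provisions might have filled the gap:

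- The 7.5.2 thresholds refer to the original GFR, so they decide who may start. They cannot be taken as an implied hold below the entry level, because the table itself continues treatment at 40–50 mL/min in patients who had to start above 60.
- Section 7.5.3 says when a dose delayed for a renal event is omitted. It gives neither a clearance threshold nor a dose.
- The oncologist's discretion in 7.2.7 and 7.5.2 concerns the choice of regimen.

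**Exposure to the rule**

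- Dosing days: 6–7 weekly, against 3 three-weekly (Days 1, 22 and 43). These count occasions on which the rule may apply, not patients affected.
- Expected cisplatin patients: 27 − 16 = 11.
- Affected: those among the 11 who are on weekly dosing with creatinine above 1.2 mg/dl and clearance of 40–50 mL/min. The documents do not give this number.

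**A proportional rule**

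Half the scheduled dose gives 100 × 0.5 = 50 mg/m² three-weekly, which reproduces the printed row, and 40 × 0.5 = 20 mg/m² weekly.

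**The case against.** The strongest reply is that nobody would read the table as a weekly rule. Section 7.5.2 treats 100 mg/m² as the full dose and ties it to a GFR above 60 mL/min, which matches the table's top row; a weekly reading would mean 100 mg/m² every week. A clinician consulting a toxicity section would not raise the dose. This stands as far as intent goes: the table was probably written for the three-weekly regimen, and a 50 mg/m² weekly dose is the less likely outcome. But that reading leaves the weekly patient without a dose, which is the other half of the point.

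It can also be said that guidance is not wholly absent. The creatinine trigger, the 24-hour urine rule and the stop below 40 mL/min work for either regimen; 7.5.3 contemplates delay and omission for renal events; the weekly entry threshold points away from full dose below 50 mL/min; and 7.5 refers the reader to the package insert. The first of these is right, and it narrows the defect to one label and one dose. The others do not state what to give at 40–50 mL/min, and the insert reference is general.

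The table as I have it also shows no row for 50–60 mL/min. A row may have been lost in conversion from PDF, so I draw no conclusion from its absence. A recovered row there would leave the legible 40–50 row unchanged.

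Finally, this is a pilot of 27 patients, weekly dosing is the non-preferred option, and few patients, possibly none, will meet the condition. That is fair, and it limits the weight of the point.

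**Conclusion.** The point holds: the rule is wrong as written for one of the two permitted regimens. Taken literally, a weekly patient at 40–50 mL/min receives 25% more than scheduled. Taken as three-weekly only, that patient has no protocol dose, and treating oncologists could choose anything from 0 to 40 mg/m². The second consequence is the more likely.

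The conclusion rests on the printed doses and on no other section supplying a weekly figure. The size of the affected subset is unknown; the expected 11 cisplatin patients assume the plan's 60% response rate. The primary endpoint, two-year locoregional control in cetuximab responders, and the sample size are untouched. It should be fixed, because it concerns the safe dosing of a nephrotoxic drug and the correction is simple.

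**What to change.** In 7.5.3.2, label the 100 and 50 mg/m² rows as applying to the three-weekly regimen, and add a weekly rule for 40–50 mL/min that cannot exceed 40 mg/m². The simplest form is to express the row as a 50% reduction of the scheduled dose, as the ototoxicity rule in the same section does: 50 mg/m² three-weekly, 20 mg/m² weekly. The 20 mg/m² figure is illustrative and does not come from the documents; the sponsor's oncologists should confirm it or specify a hold.

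Keep the creatinine trigger, the 24-hour urine rule and discontinuation below 40 mL/min, and state that they apply to both regimens. While the table is open, check that the source document covers 50–60 mL/min.

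The cost is a wording amendment to one table, with no added procedures, visits or patients.

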7.2.7 Concurrent cisplatin and EBRT

Patients receiving concurrent cisplatin EBRT will receive 100 mg/m² q 3 weeks during EBRT or alternatively, 40 mg/m² weekly during EBRT. The q 3 weeks regimen is preferable, but the weekly regimen may also be used, at the discretion of the treating medical oncologist. The EBRT technique will be identical to that used for concurrent cetuximab and EBRT. Patients will be seen and assessed weekly by radiation oncology and on a regular basis by medical oncology, how frequently depending on the cisplatin regimen.

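### During cisplatin treatment, clearance must be calculated only when creatinine exceeds 1.2 mg/dL, so some older, lighter or female patients could reach the reduce or stop bands with no calculation required

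*Combined protocol and SAP*

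**What the plan says.** Section 7.5.3.2 gives the renal rule for each scheduled cisplatin day: "If creatinine is > 1.2 mg/dl, clearance must be done in order to make dose adjustment". The second step follows from the first: "if the nomogram calculation is less than 50 mL/min, a 24-hour urine collection is mandated". A three-row table then sets the dose from clearance. Above 60 mL/min the dose is 100 mg/m², at 40-50 it is 50 mg/m², and below 40 the instruction is "Discontinue and notify PI". The table has no row for 50-60 mL/min and does not say which regimen it covers.

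Section 7.5.2 sets entry conditions. For 100 mg/m² every three weeks, "the original GFR must be > 60 ml/min". For 40 mg/m² weekly, "the original GFR must be > 50 ml/min". Both refer to the original value. Either regimen can be in use: section 7.2.7 says "the weekly regimen may also be used", at the medical oncologist's discretion.

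The schedule in section 6 has chemistries (including creatinine) and weight every week during radiotherapy, but no clearance calculation. Section 7.5.2 also advises considering a creatinine check later in the week after cisplatin. I found no other on-treatment rule that calls for clearance.

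**The concern.** The dose decisions are defined on clearance, but the screen is a single creatinine value that takes no account of age, sex or weight. At the same creatinine, an older, lighter or female patient has a much lower clearance than a younger, heavier man. Such a patient could sit in the reduce or stop band while the written rule asks for no calculation, no 24-hour urine and no dose decision. The table then has no value to act on.

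What is at stake is individual safety: cisplatin at an unreduced dose where the protocol's own table says to reduce or stop. Affected patients are plausible here. Eligibility sets no upper age limit or weight limit and allows ECOG 2. Section 2 notes that older and less fit patients often receive cetuximab instead of cisplatin, whereas section 7.2.5 assigns treatment by rash and CT response, so an older non-responder is assigned cisplatin.

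**Working it through.** The plan gives no figure to reproduce, so the check asks whether the trigger and the dose bands can disagree.

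**Inputs.** Trigger: creatinine above 1.2 mg/dL (7.5.3.2). Action limits: 50 and 40 mL/min (7.5.3.2). Baseline gates: above 60 and above 50 mL/min (7.5.2). Formula, assumed to be the nomogram: Cockcroft-Gault as printed in 5.1.5. The ages and weights below are my assumptions, because the document gives no distribution. Weight is held constant.

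**Formula.** Clearance = K / Cr, where K = (140 − age) × kg / 72, multiplied by 0.85 for women. The highest creatinine that does not trigger the rule is 1.2.

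**Step 1: who can be below a limit at creatinine 1.2?**
- Below 50: K < 50 × 1.2 = 60. That is (140 − age) × kg < 60 × 72 = 4,320 for men, or 4,320 / 0.85 = 5,082 for women. Weight must be under 61.7 kg for a man of 70, 66.5 kg for a man of 75, 67.8 kg for a woman of 65, or 72.6 kg for a woman of 70.
- Below 40: K < 40 × 1.2 = 48. That is (140 − age) × kg < 3,456 for men, or 4,066 for women. The corresponding weights are 49.4, 53.2, 54.2 and 58.1 kg.

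**Step 2: does the baseline gate prevent this?** With baseline creatinine Cr0:
- Three-weekly gate, K > 60 × Cr0. Falling below 50 needs a creatinine rise of more than 60/50, i.e. 20%, and stays untriggered only if Cr0 < 60/60 = 1.0. Falling below 40 needs a rise of more than 60/40, i.e. 50%, from Cr0 < 48/60 = 0.8.
- Weekly gate, K > 50 × Cr0. Falling below 40 needs a rise of more than 50/40, i.e. 25%, from Cr0 < 48/50 = 0.96.

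The gates narrow the gap but do not close it.

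**Step 3: examples.**

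| Patient | K | Baseline clearance | Cr at 50 mL/min | Cr at 40 mL/min | Clearance at Cr 1.2 |
|---|---|---|---|---|---|
| Man 60 y, 70 kg | 77.78 | 77.8 at 1.0 | 1.56 | 1.94 | 64.8 |
| Man 70 y, 60 kg | 58.33 | 72.9 at 0.8 | 1.17 | 1.46 | 48.6 |
| Woman 65 y, 60 kg | 53.12 | 66.4 at 0.8 | 1.06 | 1.33 | 44.3 |
| Woman 70 y, 55 kg | 45.45 | 64.9 at 0.7 | 0.91 | 1.14 | 37.9 |
| Same woman, weekly gate only | 45.45 | 50.5 at 0.9 | 0.91 | 1.14 | 37.9 |

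The first patient is not affected. The second is affected only between about 1.17 and 1.20. The 70-year-old woman is below 50 without a trigger from about 0.91 to 1.20, and below 40 from about 1.14. At an unchanged creatinine, a 10% weight loss would lower each clearance by a further 10%.

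**Step 4: ceiling on numbers.** Section 16.2 assumes a 60% response, so the expected cisplatin cohort is 27 × 0.40 = 10.8, about 11 patients. The affected subset cannot be derived.

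**Step 5: the missing band.** A man of 60 years and 70 kg at creatinine 1.4 does trigger the rule and has 77.78 / 1.4 = 55.6 mL/min, for which the table has no row. This gap exists whatever trigger is used.

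**The case against.** The case for leaving the text alone has four parts.

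- The nomogram is unnamed, and Cockcroft-Gault appears only for eligibility. This stands: every figure above is conditional on that formula.
- The table is keyed to clearance, so it can be read as governing whenever a clearance is known, with the creatinine trigger only marking when one is compulsory. That is a fair reading, but it does not produce a clearance value at creatinine 1.2 or below.
- Other safeguards exist: weekly chemistries, hydration, and the physician's assessment before each cycle (section 8). An attentive oncologist may well calculate clearance anyway. None of these requires it.
- The affected patient must be a non-responder, older or light, with a sizeable creatinine rise that still ends at or below 1.2. For the 70-year-old woman starting at 0.7, reaching 40 mL/min takes a rise of about 62% (1.14 / 0.7). This stands, and it keeps the point small.

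A reader might also infer that a weekly patient at 40-50 mL/min can simply stay on 40 mg/m², because the table's reduced dose of 50 is higher. The documents do not support this. It compares single doses on different schedules: 40 mg/m² weekly is 120 mg/m² over three weeks, against 50 for a three-weekly patient in the same band. It would also continue full weekly dosing below the level required at entry. The table may cover only the 100 mg/m² regimen or may imply a 50% cut, and the text does not say which.

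**Conclusion.** The point holds as a cheap safety improvement of low expected frequency. Followed exactly, the written rule can leave a patient on unreduced cisplatin when the protocol's own table calls for a reduction or a stop. This rests on Cockcroft-Gault being the nomogram and, for the figures shown, on constant weight and illustrative ages and weights.

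Two stronger inferences should be resisted. One is that the rule will cause overdosing in a known share of patients. The documents give no age, sex, weight or creatinine distribution, and a calculated value below 50 only leads to a 24-hour urine, so how often a dose would change is unknown. About 11 of 27 is a ceiling, not an estimate. The other is that the trial's result is at risk. The primary endpoint is measured in cetuximab responders, who are assigned cetuximab with radiotherapy, and sample size, power and alpha do not depend on this rule.

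**What to change.** Replace both the trigger sentence and the nomogram sentence in section 7.5.3.2 with: *Before every cisplatin dose, calculate Cockcroft-Gault clearance from current creatinine and weight, whatever the creatinine; if below 50 mL/min, obtain a 24-hour urine before dosing and use the measured clearance for the dose table.* This names the formula and says which value governs the dose; the current text does neither.

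Add to the table:
- Below 40 mL/min, cisplatin stops on either regimen.
- The 50 mg/m² row applies to the 100 mg/m² three-weekly regimen and never raises a weekly dose.
- A weekly dose at 40-50 mL/min, to be set by the sponsor.
- A dose at 50-60 mL/min, also to be set by the sponsor. More patients will be seen in this band once clearance is calculated at every dose, so it should be settled in the same amendment.

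**Cost.** The calculation needs no new routine test, since creatinine and weight are already scheduled weekly during radiotherapy. There will be a few more 24-hour urines and dose reductions. A collection before dosing may delay a dose by a day or more. Section 7.5.2 gives some room: "Days of administration may vary up to two days, and may vary longer if necessary due to toxicity". That allowance follows the Days 1, 22 and 43 schedule and comes before the weekly alternative, so it is not clearly available to weekly patients; the amendment should say whether it is.

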7.5.4 Concomitant Medications

Patients are discouraged from taking excessive antioxidants while on this study, as it theoretically should lessen the efficacy of radiation therapy, but this should not exclude anyone from being on study.

7.5.5 Supportive Care Guidelines

Patients are allowed to receive full supportive care therapies concomitantly during the study. No other chemotherapy, immunotherapy, hormonal cancer therapy, radiation therapy, surgery for cancer, or experimental medications will be permitted while the patients are participating in this study.

Antiemetic agents

Premedication with a 5HT3 antagonist and corticosteroid is encouraged as discussed in Section 7.4.3.1.

Colony stimulating factors (CSFs)

CSFs are not permitted as primary prophylactics. If, in the Investigator's opinion it is required in the presence of severe neutropenia (ANC $<500/\mu\text{l}$ for at least 3 days) with or without the presence of documented infection then use of CSFs must be discontinued at least 24 hours prior to the start of the next cycle of chemotherapy. If a patient develops hematologic toxicities, chemotherapy dose reduction and acute treatment of neutropenia are

recommended, rather than chemotherapy dose maintenance and pre-emptive treatment with CSFs.

Erythropoietin use is not permitted as it has been demonstrated to have a detrimental effect on HNSCC tumor control. Blood transfusions are permitted at the oncologists' discretion.

7.5.6 Adherence/Compliance

Patients will receive cisplatin q 3 weeks or weekly per their medical oncologist. They should adhere to their oncologist's recommendations (based on the protocol) re administration of cisplatin. Failure to do so may result in removal from the study.

8. Toxicity Monitoring and Adverse Event Reporting

All patients who receive one dose of protocol therapy will be evaluable for assessment of toxicity. Prior to each cycle the treating physician will fully assess the patient's condition with respect to possible treatment related toxicities. All adverse events, whether observed by the physician or reported by the patient, occurring during the active portion of therapy, or up to 30 days after the last dose of treatment will be graded by a numerical score according to the NCI's Common Terminology Criteria for Adverse Events (CTCAE), Version 4.0 (<http://ctep.cancer.gov/reporting/ctc.html>) and recorded in the patient's medical record. Grade 2 and above toxicities will be recorded.

For the purposes of reporting laboratory abnormalities, only Grade 3-4 adverse events will be recorded on the adverse event CRF pages. Grade 1-2 laboratory abnormalities will not be recorded on the adverse event CRF pages. Information entered on the adverse event CRF pages will include:

- § Specific type and duration of reaction (i.e., start and stop dates, resolution).
- § Severity/grade.
- § Relationship to study drug (causality, attribution).
- § Management of the event, if treated with medication and other actions taken to alleviate the clinical event.
- Whether or not it was considered a SAE.

A preexisting condition is one that is present at the start of the study. A preexisting condition will be recorded as an adverse event if the frequency, intensity, or the character of the condition worsens during the study period.

